# 1.5. Relevant Literature References and Prior Clinical Data Relevant to Proposed Clinical Study

The review of the scientific literature examined the current state of published information contact lens safety and myopia control with soft contact lenses. Potential applicable literature was identified through a literature search on PubMed.org dated back to 1980's, as well as through examination of review articles published on the subject. A list of relevant literature references is provided in latest version of the Investigator's Brochure for EMO Design Family Lenses.

To date, there have been only three clinical studies involving the EMO family of lenses (non-dispensing), (short-term dispensing for up to 3 days) and (non-dispensing) were pilot studies with a primary objective of evaluating the visual performances of EMO lens design prototypes in adult subjects. A total of seven lens prototypes were examined, including the EMO-114, -116, and -118 lenses that will be investigated in the current study. There were no ocular adverse events reported in these studies. For detailed information regarding prior clinical data refer to the latest version of the Investigator's Brochure for EMO Design Family Lenses.

## 2. STUDY OBJECTIVES, ENDPOINTS AND HYPOTHESES

#### 2.1. Objectives

The objective of the study is to evaluate the safety and effectiveness of three soft contact lens prototypes for controlling myopia progression by comparing to a control soft contact lens.

#### **Primary Objective:**

The primary objective of the study is to evaluate the performance of three soft contact lens prototypes for slowing myopia progression in children age 7 to 12 years old (inclusive) after 6-month of lens wear by comparing to a control soft contact lens.

#### Secondary Objective:

The secondary objective of the study is to evaluate the safety of three new soft contact lens prototypes. The evaluation of the safety of the test articles will be based on monitoring adverse events, slit lamp findings and subject reported ocular symptoms throughout the study.

#### **Other Objectives:**

Other exploratory objectives include:

- 1. Assessing visual acuity with the study lenses;
- 2. Assessing lens fit characteristics;
- 3. Assessing lens wear time compliance;
- 4. Assessing subject's responses regarding lens vision, comfort and handling performances.

In addition, the performance of the three Test lenses (EMO-114, -116, and -118) for myopia control may be evaluated and compared with the Control lens (EMO-117) for one year of lens wear, if applicable. Summary statistical analyses will be performed on safety and efficacy parameters of available 1-year data.

#### 2.2. Endpoints

#### **Primary Endpoints**

There are two co-primary endpoints in this study:

- 1. Change of axial length (AL) from baseline at 6 months;
  - Axial length (in the unit of mm) will be measured using LENSTAR LS 900 manufactured by Haag-Streit, or a similar device (e.g., IOLMaster) in selected Asian sites upon approval of the sponsor.
- 2. Change of spherical equivalent of cycloplegic auto refraction (SECAR) from baseline at 6 months

SECAR (in the unit of D) will be computed from the sphero-cylindrical refraction measured by a commercially available autorefraction such as WAM-5500 manufactured by Grand Seiko.

#### **Secondary Endpoints**

• Serious and significant ocular Adverse Events (AEs)

#### **Other Endpoints:**

- 1. Non-significant AEs and non-ocular AEs
- 2. Slit lamp findings per the ISO 11980 grading scale
- 3. Subject-reported ocular symptoms
- 4. Corneal radius of curvature measured by an autorefractor
- 5. Over-the-lens near visual acuity
- 6. Subjective best-sphere over-refraction
- 7. Number of power modification per each prescription update
- 8. Number of prescription update during the study
- 9. Lens fit characteristics
- 10. Distance logMAR visual acuity under High Luminance High Contrast (HLHC) conditions
- 11. Subjective vision, comfort, and handling scores based on the Pediatric Contact Lens User Experience (pCLUE) questionnaire.

pCLUE is a subjective questionnaire that is currently being developed specific for pediatric populations based on the existing CLUETM questionnaire for the adult population. CLUETM is a validated patient reported outcomes (PRO) questionnaire to assess patient-experience attributes of soft contact lenses (comfort, vision, handling, and packaging) in a contact-lens wearing population in the US, ages 18-65.

- 12. Lens wear time compliance
- 13. Number of visits for contact lens insertion/removal training

In addition, the following observations will be recorded or monitored throughout the study:

- 1. Subject's demographics
- 2. Subject's disposition, number and reasons for discontinuation
- 3. Number and reasons for unscheduled visits
- 4. Lens accountability, including reasons for lens dispensing or replacement
- 5. Protocol deviations
- 6. Product quality complaints

#### 2.3. Hypotheses

#### Primary Hypotheses:

After approximately 6 months of lens wear, at least one of the three Test lenses (EMO-114, -116, and -118) will be efficacious in slowing the progression of myopia compared to the Control lens (EMO-117) such that:

- 1. the change of axial length (AL) of the eye from baseline will be statistically significantly less for the Test lens compared with the Control lens.
- 2. the change of Spherical Equivalent of Cycloplegic Auto Refraction (SECAR) of the eye from baseline will be statistically significantly less in magnitude with the Test lens compared with the Control lens.

Both conditions regarding the performance of the Test lens must be met in order to meet the primary objective.

#### Secondary Hypothesis:

Secondary endpoint and all other safety endpoints will be summarized descriptively. No secondary endpoint hypothesis testing will be performed.

# **3. TARGETED STUDY POPULATION**

#### **3.1.** General Characteristics

Healthy male and female children between 7 and 12 years of age (inclusive) with best sphere refraction between -0.75D and -4.50D (inclusive), 1.00D or less astigmatism. Potential subjects can be spectacle lens wearers, current soft lens wearers, or symptomatic myopes (e.g., with complaints of blurry vision) but currently with no correction. Each study site will aim to enroll at least 50% of subjects in the age group of 7 - 9 years as well as subjects with 0.50D or more myopia progression in the past 12 months (documented or by self-report) to their best effort. There are no restrictions as to gender or race/ethnicity.

#### 3.2. Inclusion Criteria

Potential subjects must satisfy all of the following criteria to be enrolled in the study:

Inclusion Criteria after Screening:

- 1. The subject must read (or be read to), understand, and sign the Statement of Information and Assent and receive a fully executed copy of the form.
- 2. The subject's parent(s) or legal guardian(s) must read, understand and sign the Statement of Informed Consent and receive a fully executed copy of the form.
- 3. Appear able and willing to adhere to the instructions set forth in this clinical protocol.
- 4. Between 7 and 12 years of age (inclusive).
- 5. Have normal eyes (i.e., no ocular medications or infections of any type).

Inclusion Criteria after Baseline 1:

- 6. Distance subjective best-sphere refraction must be between -0.75D and -4.50D (inclusive) in each eye.
- 7. Cylindrical refraction must be 1.00D or less in each eye, by subjective sphero-cylindrical refraction.
- 8. Have sphero-cylindrical best-corrected visual acuity of 20/25 (ie, 0.8 in decimal convention or 0.10 logMAR) or better in each eye.

Inclusion Criteria after Baseline 2:

- 9. Cycloplegic objective sphero-cylindrical refraction (by auto refraction) must be between -0.75D and -4.50D in sphere and is 1.00D or less in cylinder in each eye (based on the average of 5 repeated sphero-cylindrical refraction measures).
- 10. The difference in spherical equivalent power between the two eyes must be less than 1.50D (based on the average of 5 repeated sphero-cylindrical refraction measures).

# 3.3. Exclusion Criteria

Potential subjects who meet any of the following criteria will be excluded from participating in the study:

Exclusion Criteria after Screening:

- 1. Currently pregnant or lactating.
- 2. Any systemic allergies, infectious disease (e.g., hepatitis, tuberculosis), autoimmune disease (e.g., rheumatoid arthritis), or other systemic diseases (e.g., diabetes), by the parent or legal guardian's report, which are known to interfere with contact lens wear and/or participation in the study.
- 3. Use of systemic medications (e.g., chronic steroid use) that are known to interfere with contact lens wear.
- 4. Any current use of ocular topical medication.
- 5. Any previous or planned ocular or intraocular surgery, including refractive surgery.
- 6. Participation in any contact lens or lens care product clinical trial within 30 days prior to study enrollment.
- 7. Participation in any prior myopia control clinical study in the test group.
- 8. Current or recent (within 30 days from enrollment) rigid lens wearers.
- 9. History of orthokeratology treatment or use of other ophthalmic devices (e.g., bifocal, multifocal contact or spectacle lenses) or drugs (e.g., atropine or pirenzepine) for the purpose of controlling myopia progression.
- 10. Any known hypersensitivity or allergic reaction to EyeCept® (or sponsor approved equivalent) Rewetting Drop Solution.
- 11. Relatives of employee of investigational clinic (e.g., Investigator, Coordinator, Technician).

Exclusion Criteria after Baseline:

- 12. Any ocular allergies, infections or other ocular abnormalities that are known to interfere with contact lens wear and/or participation in the study. This may include, but not be limited to, aphakia, uveitis, ocular hypertension, glaucoma, severe keratoconjunctivitis sicca, history of recurrent corneal erosions, keratoconus, keratoconus suspect, pellucid marginal degeneration, entropion, ectropion, extrusions, chalazia, and recurrent styes.
- 13. Grade 3 or greater palpebral conjunctival observations or any other Grade 2 or greater slit lamp findings (e.g., edema, corneal neovascularization, corneal staining, conjunctival injection) on the ISO 11980 classification scale.
- 14. Any previous history or signs of a contact lens-related corneal inflammatory event (e.g., past peripheral ulcer or round peripheral scar), or any other ocular abnormality that may contraindicate contact lens wear.
- 15. Any central corneal scar
- 16. Any corneal distortion resulting from ocular diseases or previous hard or rigid gas permeable contact lens wear.
- 17. Binocular vision abnormality, intermittent strabismus or strabismus.
- 18. Anterior chamber angle is Grade 2 or narrower in either eye.
- 19. IOP is 21 mmHg or higher in either eye.

#### **3.4. Enrollment Strategy**

Study subjects will be recruited from the Institution/clinical site's subject database and/or utilizing Independent Ethics Committee (IEC) or Institutional Review Board (IRB) approved materials.

# 4. STUDY DESIGN AND RATIONALE

#### 4.1. Description of Study Design

This is a multi-site, prospective, randomized, controlled, double-masked, four-arm-parallelgroup, dispensing study.

Each subject will be bilaterally fitted with one of the four types of test articles and wear lenses of the assigned lens type during the entire course of the study. Test articles will be worn a minimum 8 hours per day and 5 days per week (subjects will be encouraged to wear study contact lenses 10 hours or more per day and 7 days per week) in a daily disposable modality for a minimum of 6 months and up to 1 year\*.

There will be a total of 7 scheduled visits. Visit 1: Screening and baseline evaluation Visit 2: Baseline, randomization, lens fit and dispensing Visit 3: 1-week follow-up Visit 4: 1-month follow-up Visit 5: 3-month follow-up Visit 6: 6-month follow-up Visit 7: 1-year follow-up (optional)\*

\* The study will complete after all subjects have completed the 6-month follow-up (Visit 6). Considering the extensive enrollment period (e.g., approximately 8 months), while waiting for the last enrolled subjects to complete the 6-months follow-up, the study allows subjects enrolled at the beginning of the enrollment period to continue wearing study lenses for up to 1 year and complete the 1-year follow-up (Visit 7) before completing the final evaluation and exiting the study.

Study participants will have no access to test articles at study closure.

#### 4.2. Study Design Rationale

The study is designed as a study for proof of concept that soft contact lenses with novel optical designs have the potential for controlling myopia progression. A total of three investigational soft contact lenses will be evaluated for their safety and effectiveness of controlling myopia progression in children of 7 to 12 years of age by comparing to an FDA-cleared, non-marketed control contact lens.

Among the three Test lenses, two are of novel optical designs for myopia control (EMO-114 and EMO-118). The third Test lens (EMO-116) with an optical design simulating the MiSight lens (CE-marked for the myopia control indication, not marketed in the US, Canada or China) is included in the study to serve as a reference (positive control) for evaluating the myopia control efficacy of the two novel lens design prototypes (EMO-114 and EMO-118).

The Control lens (EMO-117) used in this study is an FDA-cleared, non-marketed soft contact lens with conventional, single-vision spherical optical design. This lens is selected as the

placebo control for evaluating the optical impact of the three Test lenses on myopia progression.

All four types of test articles are identical in all aspects (lens material, diameter, base curve, modality, and manufacturing process) except for different optical designs.

Since evaluating myopia progression of a subject and the lens effect of controlling myopia progression is longitudinal in nature, a bilateral dispensing, parallel-group study design is required. The designs of the four test articles allow the study to be conducted as a randomized, placebo-controlled, double-masked trial, which is considered to be the gold-standard for a clinical trial. Such clinical trial design and the selection of a soft contact lens as the control are recommended by the expert panel during the FDA workshop to inform the premarket evaluation of contact lenses designed to control myopia progression ([name], September 30, 2016).

For the purpose of minimizing potential seasonal effect on a subject's rate of myopia progression, the complete evaluation of the effectiveness of a Test lens typically requires at least 1 year of lens wear. The study, however, is designed to have a minimum of 6 months of lens wear follow-up and evaluates the myopia control effect of Test lenses at 6 months instead of 1 year. The reason for selecting the 6-month study duration is that based on clinical trials reported in the literature and conducted by JJVC on evaluating lenses for myopia control, it appears that the treatment effect, if any, is largest within the first 6 months treatment, and the effect appears to diminish over time. Therefore, as a first study for proof of concept of EMO lens design prototypes, a 6-month treatment period is expected to be sufficient to identify lenses that have potential myopia control effect.

#### 4.3. Enrollment Target and Study Duration

Approximately 240 subjects will be enrolled in the study with a minimum of 160 subjects (40/arm) targeted to complete the 6-month follow-up. The point of enrollment is defined as the execution of the informed consent and assent at Visit 1.

Approximately 6-8 multi-national clinical sites, including sites in the US, Canada and China will participate in the study. Each site is expected to enroll approximately 30 to 40 subjects with 20 to 32 subjects (approximately 5 to 8 subjects per arm, per site) targeted to complete the study.

The duration of study enrollment will be approximately 8 months, unless otherwise approved by the Sponsor.

Eligible subjects will be randomly assigned to one of the four study arms and complete up to six scheduled visits. Details of the visit schedule are provided in Sections 4.1 and 7.1 of the current study protocol.

The total duration of the study is estimated to be 18 months, including approximately 8 months of enrollment period.

# 5. TEST ARTICLE ALLOCATION AND MASKING

#### 5.1. Test Article Allocation

The study lenses will be worn in a bilateral and random fashion using parallel design with 4 lens types. Using a computer-generated randomization scheme provided by the study biostatistician, each subject will randomly be assigned to one of four study arms with a 1:1:1:1 ratio. Randomization will be first stratified by site. At each site, the study sample will be further stratified based on age (7 - 9 years and 10 - 12 years) and best-sphere refraction at baseline (lower than -2.00D myopia vs. -2.00D or more myopia). Each study site will aim to enroll at least 50% of subjects in the age group of 7 - 9 years.

Randomly-permuted block randomization will be used to avoid bias in the assignment of subjects to treatment, and to enhance the validity of statistical comparisons across treatment groups. Each block will contain four different lenses.

The clinical site will follow the randomization scheme provided and will complete enrollment according to the randomization list and will not pre-select or assign subjects.

Randomization must be performed at Visit 2. The following must have occurred prior to randomization:

- Informed consent and assent have been obtained from participant's parent/legal guardian and the participant
- It has been determined that the subject meets all the inclusion / exclusion criteria
- Subject history and baseline information has been collected

When the trial fitting assessment is ready to be conducted, the following steps should be followed:

- 1. Investigator or designee (documented on the Delegation Log) will consult the randomization scheme to obtain the study test article assignment for that subject prior to dispensing.
- 2. Investigator or designee will record the subject's number on the appropriate line of the randomization scheme.
- 3. Investigator or designee will pull the appropriate test articles from the study supply. All test articles that were opened, whether dispensed or not, must be recorded on the Test Article Accountability Log in the "Lenses Dispensed" section.

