#### 5.2. Masking

This study will be double-masked. Both subjects and investigators (including clinical site personnel involved in the data collection) will be masked to the identity of the investigational product during the study. Every attempt will be made to keep the other clinical trial personnel involved in the study (e.g. Data management, Biostatistician and Clinical Operations) unaware of the identity of the study lenses. The identity of the study lenses will be masked by over labeling the blister packs with a label containing the study number, lot number, sphere power, expiration date and the randomization codes. Only the personnel involved in the over labeling and the Statistician generating the randomization scheme will have access to the decode

information translating the randomization codes into test articles. The medical monitor will also have access to the decode information in case breaking the mask is necessary for the urgent medical treatment of a subject.

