2.18	Continuance (Lens Dispensing Criteria)	
 
For the subject to continue in the study, they must meet all five of the following criteria:
 
1. The subject's distance Landolt C LogMAR visual acuity with the test article measured under bright illumination and high luminance conditions with the high contrast charts must be 0.10 logMAR or better binocularly, and 0.14 logMAR or better in each eye for the test articles to be dispensed to the subjects.
 
2. Vision with the study lenses must be acceptable to the subjects.
 
3. The lens fit is acceptable OD and OS
 
4. Investigator approval. If the Investigator does not approve the dispensing of the study lens, then the study is terminated for that subject.
 
5. The subject has successfully completed the I/R training and answered all questions in the Contact Lens Checklist correctly.
 
			
2.19	Lens Dispense	
 
The lenses will be dispensed for a wearing period of 7±3 days (e.g., approximately 15 lenses per eye). The lenses will be worn as daily wear/daily disposable only.
 
At the investigator's discretion, provide the subject with rewetting drops approved in local markets (No solutions, e.g., disinfecting or storage, will be given to the subject). The study lens will be worn on a basis of a daily disposable modality.
 
Study contact lens dispensing instructions checklist:
 
Habitual contact lens wearers should wear the study lenses at least 8 hours a day. 5 days a week
 
			

-	Visit 2: Lens Fitting			
Step	Procedure	Details		

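### Section 5.1 has site staff read lens codes from a randomisation list in what read as blocks of four, and no allocation-concealment step is described

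*Combined protocol and SAP*

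**What the plan says.** Section 5.1 (Test Article Allocation) has the study biostatistician generate the scheme, and "each subject will randomly be assigned to one of four study arms with a 1:1:1:1 ratio". Strata are site, two age groups and two refraction groups, the last defined by "best-sphere refraction at baseline (lower than -2.00D myopia vs. -2.00D or more myopia". On method it says "Randomly-permuted block randomization will be used to avoid bias in the assignment of subjects to treatment" and "Each block will contain four different lenses".

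The operating steps follow. The scheme is given to the clinical site. At Visit 2 the investigator or a delegated designee looks up the assignment in it. Then "Investigator or designee will record the subject's number on the appropriate line of the randomization scheme", and the lenses are pulled from the site's stock.

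Three safeguards are stated:

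- Sites are told not to choose or assign subjects in advance (5.1).
- Consent, eligibility and baseline data must be complete before randomisation (5.1).
- Packs are coded: "The identity of the study lenses will be masked by over labeling the blister packs with a label containing the study number, lot number", followed by sphere power, expiry date and the randomisation codes (5.2). The decode is limited to over-labelling personnel, the generating statistician and the medical monitor.

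No concealment mechanism is described in 5.1, in 5.2 or in the Visit 2 procedures (7.2).

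**The concern.** Masking and concealment are different protections. Coding the packs keeps staff from knowing which lens a child wears. Concealment keeps the person entering a child from knowing which assignment comes next. Section 5.1 provides for the first and is silent on the second. Followed as written, it puts the sequence of codes in the hands of the enrolling staff.

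The instruction not to pre-select is a rule of conduct and hides nothing. Fixing eligibility first narrows the room for selection, but the site books Visit 2 (step 1.28), so the order in which eligible children reach the list remains in its hands.

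The list a child belongs to is also not fully determined. Best-sphere refraction is measured in each eye and at two visits (steps 1.8 and 2.6), and 5.1 names neither eye nor visit. A child with eyes on either side of -2.00 D fits both refraction lists, so which line applies is partly a choice.

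At stake is the comparability of each test arm with EMO-117 on axial length and refraction. The covariates in 14.5 can adjust for measured factors but not for unmeasured reasons for steering a child.

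**Working it through.** **The plan's own figure.** Section 4.3 targets 20 to 32 completers per site in four equal arms: 20/4 = 5 and 32/4 = 8 per arm per site. This reproduces the stated 5 to 8. The documents give no figure for predictability.

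**If later lines of the list can be read.** Every upcoming code is known in advance.

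**If only past codes are known.** Assume blocks of four with each code once, and one code per arm. The best guess at positions 1 to 4 is right with probability 1/4, 1/3, 1/2 and 1.

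- Average: (1/4 + 1/3 + 1/2 + 1)/4 = 2.083/4 = 52.1%, against 25% by chance.
- Certain assignments: one in four, the last of each full block.

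**Allowing for part-filled blocks.** There are 6 to 8 sites with 2 x 2 strata each, so 24 to 32 strata. Dividing 240 enrolled evenly gives 240/24 = 10 or 240/32 = 7.5 per stratum. Enrolment is counted from consent, so fewer than this may be randomised.

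| Children in stratum | Guessed correctly | Certain |
|---|---|---|
| 7 | (2.083 + 1.083)/7 = 45% | 1/7 = 14% |
| 8 | 4.167/8 = 52% | 2/8 = 25% |
| 10 | (4.167 + 0.583)/10 = 47.5% | 2/10 = 20% |

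**Would larger blocks solve it?** The same best-guess rule was simulated with the block size known to the guesser. Blocks of 8 give about 47% correct and 14% certain; blocks of 12 give about 44% and 10%. The gain is modest, and at 7.5 to 10 children per stratum a single block of 8 nearly fills the stratum, so balance may suffer. How assignments are released matters more than block size.

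**Stratum definition.** Best-sphere eligibility is -0.75 to -4.50 D in each eye (3.2, criterion 6). Eyes at -1.75 D and -2.25 D both qualify, yet fall on opposite sides of the -2.00 D cut. Criterion 10, "The difference in spherical equivalent power between the two eyes must be less than 1.50D", does not settle the matter. It applies to cycloplegic autorefraction and not to the subjective best-sphere value used for stratifying, and a gap of 0.50 D is well inside 1.50 D in any case. The share of such children cannot be obtained from the documents.

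**The case against.** The strongest reply is that this is silence in the protocol and not a demonstrated failure. Several parts of that reply stand.

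- **Visibility.** A reader might infer that later lines are open to view. The text says only that staff consult the scheme and mark a line; a separate procedure could cover the rest. The supportable statement is that no concealment is described.
- **Block size.** Four is the natural reading, but two of each lens in a block of eight would also fit the words.
- **Codes are not lenses.** A reader might infer that sites can pick out the control lens and steer children. The documents do not say whether an arm has one code or several. Several would weaken guessing from past codes, though not reading ahead. Section 1.4 says only that vision with the EMO designs may differ from that with a spherical lens. Section 1 reports satisfactory vision with EMO-114 and EMO-118, and all arms share the same dispensing criteria. A site enrolling 30 to 40 children sees about 7.5 to 10 per lens.
- **Opportunity.** At 7.5 to 10 children per stratum over 8 months, each list receives about one child a month, which limits swapping. No text says the list reader is also the person who books visits.
- **Step 2.18.** A reader might add the investigator's power to decline dispensing: "Investigator approval. If the Investigator does not approve the dispensing of the study lens, then the study is terminated for that subject". That decision comes after assignment at step 2.7, so it is not a concealment matter and better concealment would not alter it.
- **Purpose.** This is a proof-of-concept pilot whose sample size was not set by power (4.2, 14.2).

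These points limit what can be claimed. They do not supply the missing step. If a concealment procedure exists elsewhere, 5.1 should state it.

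**Conclusion.** The point holds as a gap in the described procedure: the site holds, reads and marks the list, the blocks read as four, and nothing in the documents conceals the next assignment. Upcoming codes could be seen outright. Alternatively, with blocks of four, one code per arm and past codes known, they could be guessed 52% of the time (about 45% to 52% at the stratum sizes expected here), against 25% by chance.

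These percentages concern codes. Turning them into directed selection needs the further step of working out what a code means, which the documents make possible but do not show to be likely. It is tempting to multiply a steered fraction by a difference in eye growth to get a bias in millimetres. Neither input is in the documents, so the size of any bias is unknown. The amendment is justified because it removes an avoidable risk at little cost, not because bias has been shown.

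**What to change.** Amend 5.1 as follows.

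1. Replace consultation of the on-site list with release of one assignment at a time, after eligibility is confirmed and the child is irrevocably registered at Visit 2. Either a randomisation form in the existing EDC system (15.1) or sequentially numbered opaque sealed envelopes for each stratum would serve.
2. Do not disclose the block size to sites: take the block sentence out of the protocol text they receive and keep it in the statistician's restricted specification. Staff who have read the present text may still guess from remembered codes; the release step stops reading ahead in any case.
3. Define the refraction stratum from one value, for example the mean of the two eyes' best-sphere refraction at Visit 2 (step 2.6).

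The cost is a protocol amendment plus small set-up work for the EDC form or the envelopes. That the EDC system can host such a form is an assumption; envelopes are the fallback. No extra subjects, visits or staff are needed.
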